## Chapter 1: Study Synopsis

### Purpose of the Investigation

Myopia affects approximately one-third of the United States population (Vitale et al. 2008), which is an increase from 25% of the population reported in the 1970s and 1980s (Sperduto et al. 1983; Vitale et al. 2009). Although blurred distance vision caused by myopia is relatively easy to correct with spectacles, contact lenses, or refractive surgery, myopia costs the United States approximately \$4.6 billion annually (Javitt and Chiang 1994), high myopia is associated with increased risk of glaucoma (Loyo-Berrios and Blustein 2007; Lee et al. 2008), retinal detachment (Hyams and Neumann 1969; Eye Disease Case-Control Study Group 1993), chorioretinal atrophy (Curtin 1985), and decreased quality of life (Rose et al. 2000; Erickson et al. 2004; Chen et al. 2007). Thus, slowing the progression of myopia could potentially affect a large proportion of the population and reduce the negative side effects that accompany the disease.

Both atropine and soft bifocal contact lenses have been shown to slow myopia progression, and both can cause changes in the thickness of choroid (Read et al. 2010; Chakraborty et al. 2012; Chakraborty et al. 2013; Nickla et al. 2013), which has been suggested to serve as a signal mediator to regulate eye growth. But the relationship between these mechanisms is unclear. The central hypothesis to be tested is that atropine and soft bifocal contact lenses each exert their anti-progression actions through a common pathway that involves the choroid. If this is correct, then adding atropine treatment to soft bifocal contact lens wear will lead to a more effective slowing of myopia progression than prescribing soft bifocal contact lenses alone due to the additive effects in the common pathway. Determining whether these hypotheses are true will have significant implications for future studies to develop and test new therapeutic regimes that optimize the effect of myopia control through combined pharmacological and optical interventions.

## Chapter 2: Specific Aims

I propose a clinical study in patients with myopia to investigate the effect of a novel clinical intervention on myopia progression. Atropine, a non-selective muscarinic receptor antagonist, provides the most effective myopia control in humans when prescribed in 0.5% or 1% concentration. However, the side effects – loss of accommodation and pupil dilation – make it impractical for clinical use. Recently, low concentration atropine (0.01%) was shown to slow myopia progression by about 60% while significantly mitigating side effects in children. The precise site of action involved in slowing myopia progression with atropine remains controversial. Some authors state that atropine may slow myopia progression through antagonist effects on retinal muscarinic receptors, but others suggest that atropine may slow myopia via non-muscarinic and non-retinal mechanisms. Center distance design soft bifocal contact lenses have also been shown to slow myopia progression in children by an estimated 40% with few side effects. The mechanism for this treatment effect is most likely the myopic defocus (light focused in front of the retina), a robust growth-inhibiting signal, presented to the retina by the add (near) power of the contact lens.

Both atropine and optical defocus can cause changes in the thickness of choroid, which has been suggested to serve as a signal mediator between retina and sclera to regulate eye growth. Intravitreal injection of atropine in chicks results in rapid, transient choroidal thickening and slowed axial elongation. Additionally, the choroid thickens and thins in response to short-term optically induced myopic and hyperopic defocus, respectively. We therefore postulate that in response to the signal cascades triggered by atropine and soft bifocal contact lens wear, the choroid adjusts its thickness and transfers growth-modulating signals to sclera.

My central hypothesis is that pharmacological and optical treatments exert their anti-myopia actions through a common pathway that involves the choroid. I propose that adding atropine treatment to soft bifocal contact lens wear will lead to a more effective slowing of myopia progression than prescribing soft bifocal contact lenses alone due to the additive effects in the common pathway. Alternatively, if we find that combined treatment is no more effective than soft bifocal contact lenses alone, that would suggest a saturated effect of this shared mechanism.

To test these hypotheses, I will enroll 52 myopic children aged 7 to 11 years into a treatment protocol of wearing soft bifocal contact lenses in combination with daily administration of one drop of 0.01% atropine for three years. The rates of myopia progression and axial elongation will be compared to the rates in age-matched subjects who are receiving treatment with only soft bifocal contact lenses in the Bifocal Lenses In Nearsighted Kids (BLINK) Study (U10EY023208). The BLINK Study is a multi-center, randomized clinical trial chaired by my primary mentor, and it was designed to test the hypothesis that the peripheral myopic defocus produced by the add power of soft bifocal contact lenses is responsible for slowing myopic eye growth.

**Aim 1. To test whether the combined treatment of 0.01% atropine and soft bifocal contact lens wear produces slower myopia progression and axial elongation compared to soft bifocal contact lenses alone over 3 years.** I will compare the three-year change in spherical equivalent refractive error and axial length of subjects undergoing the combined treatment to age-matched subjects wearing only soft bifocal contact lenses in the BLINK Study.

**Aim 2. To test whether early changes in choroidal thickness can be used as predictors of long-term myopia progression / axial elongation.** I will measure the change in choroidal thickness from baseline to 3 weeks in the subjects receiving combination treatment and in the BLINK Study subjects using soft bifocal contact lenses alone. I will then determine whether the amount of 3-week change in choroidal thickness correlates with the 3-year rate of myopia progression / axial elongation in each group.

**Scientific & Clinical Impact:** The results of this study will have significant implications for future studies to develop and test new therapeutic regimes that optimize the effect of myopia control through combined pharmacological and optical interventions. The outcomes will also aid in understanding the potential role of short-term changes of choroidal thickness in long-term regulation of myopia progression and ocular growth.

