### Chapter 3: Study Design

This proposed experiment is an ancillary study of a multi-center, randomized clinical trial Bifocal Lenses In Nearsighted Kids (BLINK) Study (U10EY023208), which compares myopia progression rate between subjects wearing single vision contact lenses and those wearing soft bifocal contact lenses. The BLINK Study will enroll 294 myopic children aged 7 to 11 years at two clinical centers: The Ohio State University (OSU) College of Optometry and The University of Houston College of Optometry (UHCO).

The subjects in the BLINK Study will be randomly assigned to wear either single vision soft contact lenses or soft bifocal contact lenses with either a +1.50 D add or +2.50 D add power for at least three years, with 49 subjects in each treatment arm at each clinical center. This proposed study will recruit one group of 52 additional subjects that meet BLINK eligibility criteria and that are age-matched with a comparison group -- 49 BLINK study participants who are wearing soft bifocal contact lenses with +2.50 D add power.

The subjects in this proposed study will wear soft bifocal contact lenses in combination with daily administration of 0.01% atropine for three years. The rates of myopia progression and axial elongation will be compared to those in the comparison group in the BLINK Study. The protocol for the outcome measures in this proposed project is consistent with the BLINK Study.

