## Chapter 4: Statistical Analysis Plan

The sample size calculations for all Specific Aims were performed using PASS 2005 (Hintze J, 2007) software using  $\alpha = 0.05$  and  $\beta = 0.20$  (power =80%) and then combined to determine the optimal sample size to address all of the aims. Estimates of sample size were computed for each specific aim, as follows:

**Specific Aim 1:** To test whether the combined treatment of 0.01% atropine and soft bifocal contact lens wear produces slower myopia progression and axial elongation compared to soft bifocal contact lenses alone over 3 years.

For Aim 1, the sample size is driven by the desired difference in spherical equivalent progression between the two groups. This difference needs to be of a magnitude that is considered clinically relevant. [name] and colleagues showed that the mean ( $\pm$  SD) myopia progression of single vision soft contact lens wearers was  $-1.29 \text{ D} \pm 0.71$  over three years ([name] et al. 2008). The proposed myopia progression in the +2.50 D add soft bifocal group for the sample size calculation of the BLINK Study based on a treatment effect of 50% was  $-0.65 \text{ D}$ . A reasonable reduction in myopia progression from the addition of atropine to the +2.50 D add bifocal lenses would be about  $0.33 \text{ D}$ , an additional reduction of 50%. Using a standard deviation of  $0.71 \text{ D}$  and taking into account the pair-matched design, the sample size for this aim would be 39 subjects per group.

**Specific Aim 2:** To test whether early changes in choroidal thickness can be used as predictors of long-term myopia progression / axial elongation.

For Aim 2, the correlation between choroidal thickness and refractive error / axial length ranges from 0.35 to 0.74 based on previous studies (Nishida et al. 2012; Flores-Moreno et al. 2013; Vincent et al. 2013). A sample size of 44 per group will allow for detecting a correlation of 0.41 between short-term changes in choroidal thickness and long-term myopia progression / axial elongation.

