### Sample Size Conclusion

Using the maximum required sample size (39 subjects for aim 1, and 44 for aim 2) and adjusting for 18% loss to follow-up gives a total sample required of **52**.

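### Aim 2 asks about prediction but plans only an unadjusted correlation, which can be significant while barely narrowing a child's predicted course and cannot show added value over baseline age and refraction

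*Combined protocol and SAP*

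**What the plan says.** Chapter 2 states Aim 2 as "To test whether early changes in choroidal thickness can be used as predictors of long-term myopia progression / axial elongation". Choroidal thickness change from baseline to 3 weeks is to be measured in the combination group and in the BLINK lens-only group. The analysis is then one sentence: "I will then determine whether the amount of 3-week change in choroidal thickness correlates with the 3-year rate of myopia progression / axial elongation", done separately in each group.

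Chapter 4 repeats the aim and adds only its sample size. The planning basis is that "the correlation between choroidal thickness and refractive error / axial length ranges from 0.35 to 0.74 based on previous studies", and "A sample size of 44 per group will allow for detecting a correlation of 0.41". The chapter sets alpha at 0.05 and power at 80% for all aims, without saying whether tests are one- or two-sided.

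The document gives no prediction model, measure of prediction error, covariate adjustment or confidence-interval criterion for Aim 2. It also gives no smallest r or R² that would count as useful. Age and cycloplegic refraction are both obtained at Visit 1 (Chapter 5; Table 6-2).

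**The concern.** The aim speaks of using early choroidal change as a predictor. The planned evidence is whether a correlation differs from zero. These are different questions. With a few dozen children, a correlation can be significant while a child's expected three-year change stays almost as uncertain as without the scan.

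A raw correlation also ignores what the clinician already knows. If choroidal change tracks baseline age or refraction, it could correlate with progression and add nothing to them. The plan has the data to check this but does not say that it will.

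At stake is how the Aim 2 result can be worded. The planned test can support an association. It cannot support a statement about predictive use, in either direction.

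**Working it through.** **Inputs.** From Chapter 4: alpha 0.05, power 80%, n = 44 per group, r = 0.41, SD of three-year progression 0.71 D, cited correlations 0.35 to 0.74. From the Sample Size Conclusion: 52 enrolled, 18% loss. From Chapter 3: a comparison group of 49.

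**1. Reproduce the plan's figure.** By Fisher's z, n = ((z_α + z_power) / atanh r)² + 3.
- Two-sided: ((1.960 + 0.842) / atanh 0.41)² + 3 = 44.4, which matches 44.
- One-sided: 35.6, which does not match.

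The test is therefore taken as two-sided. Power at n = 44 and r = 0.41 is 79.7% by Fisher's z and 80.6% by the t test. The sample size stands.

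**2. Smallest significant correlation.** r = t / √(n − 2 + t²), with t the 97.5% point on n − 2 degrees of freedom. At n = 44, r = 0.297 and R² = 8.8%.

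**3. What that does to one child's range.** The half-width of the 95% range is 1.96 × SD × √(1 − r²), so the narrowing is 1 − √(1 − r²), whatever the SD. Without the scan, 1.96 × 0.71 = 1.39 D.

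| r | R² | Half-width (D) | Narrowing |
|---|---|---|---|
| 0.297 (significance limit) | 8.8% | 1.33 | 4.5% |
| 0.35 (low end of cited range) | 12.2% | 1.30 | 6.3% |
| 0.41 (planned) | 16.8% | 1.27 | 8.8% |
| 0.74 (high end of cited range) | 54.8% | 0.94 | 32.7% |

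A 20% narrowing needs r = 0.60. For scale, the plan assumes a mean progression of 0.65 D in the +2.50 D add group.

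**4. New children.** The figures above are in-sample. At r = 0.297 the leave-one-out R² is approximately 1 − 0.912 × (1/(1 − 2/44))² / (44/43)² = 0.044. Since 1 − √(1 − 0.044) = 0.022, the narrowing for a new child is about 2%.

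**5. Precision.** If r = 0.41 is observed at n = 44, the Fisher interval is 0.13 to 0.63, so R² could lie anywhere from 2% to 40%.

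**6. Sensitivity to completers.** 52 × 0.82 is about 43 and 49 × 0.82 is about 40. The significance limit is then r = 0.301 (4.6% narrowing) and r = 0.312 (5.0%). The conclusion does not move.

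**7. Number of correlations.** Two groups and two outcomes give four tests, with no multiplicity rule. If the four were independent and no association existed, the chance of at least one significant result would be 1 − 0.95⁴ = 18.5%. It is lower when the outcomes are correlated: about 14% in a simulation with the two outcomes correlated 0.8.

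**8. What possible remedies would cost.** Simulation at n = 44 and true r = 0.41, with normal data and baseline covariates explaining 9% of variance and independent of choroidal change (these last are assumptions, not plan figures):
- correlation test significant: about 80%;
- adjusted coefficient for choroidal change significant: about 82%;
- bootstrap interval for the reduction in leave-one-out error excludes zero: about 17% when paired errors are resampled, about 35% when the models are refitted in each resample.

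**The case against.** The best defence is that Aim 2 is about mechanism. Chapters 1 and 2 frame the choroid as part of a shared pathway, and the impact statement speaks of understanding its role in eye growth. An earlier variable associated with a later one is often loosely called a predictor. The plan says openly that it will correlate and powers for a correlation, so a reader can see what was tested. For a first look at mechanism, a correlation is a reasonable test. All of that stands, and it is why the correlation should stay.

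It does not remove the mismatch. The aim is worded as use, in both Chapter 2 and Chapter 4, and nothing in the plan connects the test to that wording or sets the scan against baseline information.

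Three stronger readings are tempting, and the documents do not support them:
- *Any significant r will be announced as a clinically usable predictor.* The plan contains no such reporting rule and no intention to manage a child by the scan.
- *The scan has almost no predictive value.* The 4.5% figure belongs to the bare significance limit. The planned effect gives 8.8%, and the top of the cited range gives 32.7%. That range concerns thickness against refractive error or axial length, not early change against later progression, so the document leaves the true value open.
- *Aim 2 should be decided on prediction error.* Requiring a bootstrap interval to exclude zero would rarely be met at the planned effect (step 8) and would leave the aim badly underpowered.

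**Conclusion.** The point holds as a gap between the question and the test. A significant Aim 2 correlation is compatible with a narrowing of one child's prediction range as small as 4.5%, and with 8.8% at the effect the study is powered for. An unadjusted correlation cannot show whether the scan adds anything to baseline age and refraction.

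The conclusion rests on a two-sided 5% test, inferred from reproducing 44, and on approximately normal data. The dioptre figures use an SD that Chapter 4 takes from single vision lens wearers; the percentages do not depend on it. They describe the range with no covariates, so they do not measure the gain over a baseline model. No figure for that gain can be derived from the documents. Whether 4.5% or 8.8% is too little is a matter of judgement.

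This is a minor, inexpensive improvement. The 44 per group, the data collection, Aim 1 and the primary outcome are unaffected.

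**What to change.** Keep the correlation as the powered test for Aim 2 and report r with its 95% interval, not only its p-value.

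In Chapter 4, add for each group and each outcome a regression of three-year change on baseline age and baseline refraction, fitted with and without the 3-week choroidal change. Report:
- the adjusted coefficient for choroidal change with its 95% interval;
- the change in leave-one-out prediction error between the two models;
- the resulting prediction range for one child, in dioptres and in millimetres.

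State in advance that a significant correlation will be described as an association, and that predictive use will be discussed only in light of the added value over baseline and the width of the prediction range. Do not make a bootstrap interval for the error reduction the decision rule.

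The cost is a paragraph in the plan and a short analysis of data already being collected, assuming the same baseline variables are available for the BLINK children. In the simulation the adjusted coefficient keeps about the same power as the correlation. The drawback is a more modest conclusion if the correlation proves weak.

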### Reason for Measuring

[figure not shown]
Studies have reported changes in choroidal thickness in response to optical defocus. We will investigate whether changes in choroidal thickness occur over in the control and treatment groups. OCT images will be collected through a non-dilated pupil. Because choroidal thickness changes have been reported to occur rather quickly when the eye is exposed to a change in defocus, all choroidal thickness measurements will be made immediately after removing the child's study contact lens from the right eye. Measurements will be made at Visits 2, 3, 5, 7, and 9.

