### Setting the Reference Image

This should only be done at Visit 2 after saving the OCT images. Setting a reference image maximizes the repeatability of OCT images that are acquired at subsequent visits when using the “Follow-Up” mode. To set the reference image used in Follow-Up mode, do the following:

[figure not shown]
1. Select the best scan acquired at Visit 2 to use as the reference image. Right click on the baseline OCT scan thumbnail (Figure 14-11), select “Progression” and then select “Set Reference”

Figure 14-11: Setting the reference image.

2. A red and black square can now be seen in the bottom left side of the thumbnail (Figure 14-12) indicating that it is a reference image that can be selected when using Follow-Up mode at return visits.

Figure 14-12: Reference image.

[figure not shown]

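### Aim 2 plans only a raw correlation of 3-week choroidal change with 3-year progression; a regression that also includes Visit 2 thickness should be prespecified beside it

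*Combined protocol and SAP*

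**What the plan says.** Chapter 2 defines the Aim 2 predictor as a difference: "I will measure the change in choroidal thickness from baseline to 3 weeks". The analysis is then to "determine whether the amount of 3-week change in choroidal thickness correlates with the 3-year rate of myopia progression / axial elongation in each group".

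Chapter 4, Specific Aim 2, contains a sample size only: "A sample size of 44 per group will allow for detecting a correlation of 0.41 between short-term changes in choroidal thickness" and 3-year progression or elongation. The supporting evidence given there is that "the correlation between choroidal thickness and refractive error / axial length ranges from 0.35 to 0.74 based on previous studies". That range describes the level of thickness, not its change. No regression model or covariate is named for Aim 2 in Chapter 4 or elsewhere.

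Chapter 14 fixes where the change starts. Under Reason for Measuring it states "Measurements will be made at Visits 2, 3, 5, 7, and 9", and Table 6-2 likewise shows no choroid scan at Visit 1. Under Setting the Reference Image the instruction is "Select the best scan acquired at Visit 2 to use as the reference image". The early change is therefore Visit 3 minus Visit 2, and starting thickness is already scheduled for collection.

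**The concern.** A change score carries information about where it started. If eyes with thicker choroids at Visit 2 respond by more (or fewer) microns, and thickness itself goes with faster or slower progression, the raw correlation mixes two statements: that early response predicts progression, and that starting thickness predicts progression. One scan would show the second without any treatment response.

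The plan itself gives a reason to take the second statement seriously. It cites correlations between thickness level and refractive error or axial length, and the 3-year changes in those two quantities are the Aim 2 outcomes. Chapter 2 presents Aim 2 as evidence on the part that short-term choroidal change plays in long-term eye growth, so the distinction affects how a positive result would be read. The mixing can also work the other way and hide a real effect of change.

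**Working it through.** **Inputs from the plan (Chapter 4).** n = 44 per group, detectable r = 0.41, alpha 0.05, power 80%. Sidedness is not stated; two-sided reproduces the figure.

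**Inputs not in the documents (assumed).** Correlation of Visit 2 thickness with the 3-week change (change-level): 0.1 to 0.5. Correlation of Visit 2 thickness with the 3-year outcome (level-outcome): 0.2 and 0.35. The 0.35 is borrowed from the low end of the plan's range for level against refractive status, because no figure for progression is given.

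**Step 1: the plan's figure.** n = ((1.960 + 0.842)/atanh(0.41))² + 3 = 44.4. Power at n = 44 is 79.7%. The stated 44 reproduces.

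**Step 2: level passing as change.** If change has no effect of its own, the expected raw correlation is change-level × level-outcome. With d = atanh(r) × √(44 − 3), the rejection rate is Φ(d − 1.96) + Φ(−d − 1.96). For an error-free scan:

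| Change-level | Level-outcome | Raw r | Raw test rejects |
|---|---|---|---|
| 0 | any | 0 | 5.0% |
| 0.1 | 0.35 | 0.035 | 5.6% |
| 0.3 | 0.2 | 0.060 | 6.7% |
| 0.3 | 0.35 | 0.105 | 10.4% |
| 0.5 | 0.2 | 0.100 | 9.8% |
| 0.5 | 0.35 | 0.175 | 20.5% |

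With level in the model the rate is 5.0% in every row. A negative change-level correlation of the same size gives the same raw-test rates.

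**Step 3: level masking change.** Let the standardised coefficients be 0.41 for change and 0.35 for level, with change-level −0.3.
- Raw r = 0.41 − 0.3 × 0.35 = 0.305, so power is about 52%.
- Level-outcome correlation = 0.35 − 0.3 × 0.41 = 0.227. Partial r = (0.305 + 0.3 × 0.227)/√((1 − 0.09)(1 − 0.227²)) = 0.402, so adjusted power (n − 4 = 40) is about 77%.
- If level acts in the opposite direction, raw r = 0.41 + 0.105 = 0.515 and nothing is hidden.

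**Step 4: scan error.** Write Visit 2 = T + e2 and Visit 3 = T + D + e3, with T of variance 1, SD of true change D equal to 0.2 and reliability 0.95 (all assumed).
- Error variance = 0.05/0.95 = 0.0526. Variance of observed change = 0.04 + 2 × 0.0526 = 0.145.
- With true change-level 0.3 and level-outcome 0.35, raw r = 0.2 × 0.3 × 0.35/√0.145 = 0.055. The raw test rejects 6.4% and the adjusted test 6.2% (partial r 0.052).
- With true change unrelated to level, raw r = 0 and the raw test holds 5.0%. The adjusted test rejects 6.1%. Shared scan error makes observed change and level correlate at −0.135, and observed level-outcome is 0.35 × √0.95 = 0.341. Partial r is therefore 0.135 × 0.341/√((1 − 0.135²)(1 − 0.341²)) = 0.049.

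**Step 5: precision.** With no effect of change and an error-free scan, the adjusted/unadjusted ratio of slope standard errors is √[(1 − level-outcome²)/(1 − raw r²)]/√(1 − change-level²). At level-outcome 0.35 it is 0.94, 0.99 and 1.10 for change-level 0, 0.3 and 0.5. At 0.2 it is 0.98, 1.03 and 1.14.

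**The case against.** **A raw correlation may be all that Aim 2 needs.** The aim asks whether early change can serve as a predictor, and a raw correlation answers that. Independence from starting thickness is a further question. This stands as a reason to keep the raw correlation. It does not cover a reading in which the response itself carries the information.

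**The plan is silent; it has not chosen to leave level out.** Chapter 4 gives sample sizes and no analysis model for either aim. That is correct: adjustment is not ruled out. The raw correlation is still the only Aim 2 analysis written down, and a covariate chosen after the results are seen would be less credible.

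**The cited correlations are the wrong quantity for sizing.** They concern refractive status, not 3-year change, and the Bibliography titles of two of the three studies refer to high myopia, whereas Chapter 5 admits −0.75 to −5.00 D. This stands, and it is why the upper end of that range is not used here. At low assumed values the excess is negligible.

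**Scan error argues against relying on adjustment alone.** A reader might infer that error in the shared Visit 2 scan by itself creates a false signal in the raw correlation, or that adjusting always restores a 5% test. Step 4 supports neither. When true change is unrelated to level, it is the adjusted estimate that picks up the small false signal.

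**Precision.** A reader might also infer that leaving level out necessarily costs precision. Step 5 shows gains and losses depending on correlations that the documents do not give, so no general statement is warranted.

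**Conclusion.** The point holds as a gap in what Aim 2 can conclude. As written, a positive raw correlation cannot be separated from an effect of starting thickness, and a null one could hide a real effect of change. Both problems require Visit 2 thickness to be related to the true 3-week change and also to 3-year progression; if either relation is absent, the raw test keeps its 5% level.

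The size is modest over the lower assumed values: about 7% false positives at level-outcome 0.2 and about 10% at 0.35, with change-level 0.3 and an error-free scan. At reliability 0.95 the raw and adjusted tests reject about equally often (6.4% and 6.2%). Larger figures need stronger assumed correlations. The documents do not supply them, and their cited range is for a different relation.

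The documents therefore support reporting the adjusted analysis beside the raw one. They do not support replacing the raw correlation, or a claim that the planned test is badly miscalibrated.

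**What to change.** In Chapter 4, Specific Aim 2:

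1. Keep the raw correlation of the Visit 2 to Visit 3 choroidal change with the 3-year outcome in each group.
2. Prespecify beside it, in each group, a linear regression of 3-year change in spherical equivalent on that choroidal change with Visit 2 thickness as covariate, and the same model for 3-year change in axial length.
3. State that early change will be said to predict beyond starting thickness only if the adjusted estimate supports it.
4. Report both estimates, noting that error in the Visit 2 scan can leave a small false signal in the adjusted one (about 6% rejection at reliability 0.95 and level-outcome 0.35, both assumed).

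The cost is a short addition to the text and one degree of freedom per model. No further visits, scans or children are needed. For the comparison group this relies on the statement in Chapter 3 that outcome procedures match those of the BLINK Study, so that its Visit 2 scans are available.
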